#### 9.4 Regulatory and Ethical Considerations

#### 9.4.1 Data and Safety Monitoring Plan

The faculty advisor will oversee all aspects of safety monitoring. These include the supervised fitting and collar education under observation of research team position and the reporting of any adverse events during the at home phase.

The faculty advisor will monitor and review the study progress, subject safety, and the accuracy and security of the emerging data.

#### 9.4.2 Risk Assessment

#### Not Greater than Minimal:

- Psychological
  - Wearing the collar might be embarrassing for some patients. This is averted through a flexible at home protocol in which they are only asked to wear the collar on an as needed basis for symptomatic relief and report their efficacy. Patients will be allowed to withdraw from the study at any time.
- Confidentiality
  - Any study has potential consequences a breach of confidentiality, this study will avoid those consequences through maintenance of the data in a password protected REDCAP database accessible only to the research team, all of whom are HIPAA certified.
- Discomfort
  - The device is FDA approved for contact sports, and there are no adverse risks for the indicated population. However there is a possibility that patients will feel discomfort when wearing it. Care will be made to ensure the fitting is optimize the patient's needs. Possibility of mild discomfort if collar used incorrectly; this will be averted by counseling patients to not use the collar while sleeping and by fitting the collar correctly to the neck circumference of the subject at the initial visit.

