#### 1.1 Name and Description of Investigational Product or Intervention

The current FDA approved internal jugular vein compression collar, marketed as the Q collar, is manufactured by Q30 Innovations Home. It is designed to be worn around the neck of individuals aged 13 and older. It functions by lightly compressing the internal jugular vein's bilaterally, safely increasing intracranial volume and intracranial pressure. The FDA approved neck collar device is made of a thermoplastic elastomer that is specifically fitted to an individual to provide mild internal jugular vein compression. The product was developed and confirmed with ultrasonography to confirm appropriate fit and compression of the vein based on an athlete's neck circumference.

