#### 1.3 Relevant Literature and Data

Pulsatile Tinnitus: Overview, Pathophysiology, Diagnosis

Pulsatile Tinnitus is the auditory perception of rhythmic noises in time with the heartbeat. It can be either vascular or nonvascular in origin, and vascular presentations are divided into venous and arterial etiologies. In vascular etiologies, the symptomatic presentation is a consequence of turbulence in vasculature near the cochlea, hence the synchronization with pulse. This condition can have significant adverse effects on patient quality of life, leading to insomnia, difficulty concentrating, impaired audition, and mental health deterioration. Venous abnormalities are the most common causes of pulsatile tinnitus, particularly structural and flow abnormalities in one or multiple intracranial or extracranial venous structures secondary to intracranial hypertension or anatomical variation. Non-invasive imaging is an effective means of diagnosing pulsatile tinnitus, successfully identifying relevant phenomena in 40% to 70% of cases. Furthermore, physical exam alone can distinguish venous causes from other ideologies of pulsatile tinnitus. Specifically, relief of symptoms upon temporary manual neck compression of the ipsilateral IJV detects venous etiology with 93% sensitivity, a finding that is replicated with less sensitivity by a Valsalva maneuver or by turning the patient's head toward the side lateralizing with pulsatile tinnitus.9-10

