# 3.3.2 Subject Exclusion Criteria

- Increased presence of acid in the body or excessive blood alkalinity
- Open head injury (including in or around the eye) within the past six months
- Pseudotumor cerebri (false brain tumor)
- Presence of brain or spinal shunt
- Known seizure disorder
- Known airway obstruction
- Increased likelihood of blood clotting (coagulation)

- age <18
- unable to provide written consent,
- history of neurological deficits,
- previous cerebral infarction (blockage or narrowing in the arteries supplying blood and oxygen to the brain)
- severe head trauma
- medical contraindications to restriction of blood outflow via the internal jugular veins
- glaucoma (narrow angle or normal tension increased pressure in the eyes),
- hydrocephalus (increased fluid on the brain)
- recent penetrating brain trauma (within 6 months),
- known carotid hypersensitivity
- known increased intracranial pressure
- idiopathic intracranial hypertension
- known intracranial vascular malformation (e.g. aneurysm, arteriovenous malformation, cavernoma)
- central vein thrombosis
- not tolerating initial fitting of collar.
- Known pregnancy (this is not a direct contraindication but is being made out of an abundance of caution)
- Inability to speak or comprehend English (this pilot study does not have funding for translators)

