# 6.3.3 Safety Analysis

Adverse events are not expected; however, all subjects entered into the study at Visit 1 will be included in the safety analysis. The frequencies of AEs by type, body system, severity and relationship to study drug will be summarized if at all present. SAEs (if any) will be described in detail.

AE incidence will be summarized along with the corresponding exact binomial 95% twosided confidence intervals.

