#### 9.4.4 Risk-Benefit Assessment

Given that the device is approved by the FDA in a different setting, that is, contact sports, and given that use of the device in this application will follow all FDA recommendations regarding duration, use, and contraindications, we anticipate minimal risk to participants in the study. The benefits for participants are high given that it is likely the Color will be effective based on the principle of its use aligning directly with the chief diagnostic physical exam findings of this condition, that is, relief of symptoms upon light compression of the internal jugular vein. Therefore, in light of these observations, and given the fact that this condition has limited treatment options outside of surgery, we determine it worthwhile to proceed with the study.

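### The risk section does not address the rise in intracranial pressure attributed to the collar; the protocol text names no pressure symptom and schedules no adverse event item at Visit 2

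*Combined protocol and SAP*

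**What the plan says.** **Device effect.** Section 1.1 describes the collar as compressing both internal jugular veins, "safely increasing intracranial volume and intracranial pressure".

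**Disease.** Section 1.3 describes the venous abnormalities behind pulsatile tinnitus as "secondary to intracranial hypertension or anatomical variation".

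**Eligibility.** Section 3.3.2 excludes "known increased intracranial pressure" and "idiopathic intracranial hypertension", along with pseudotumor cerebri, hydrocephalus, shunts, glaucoma, central vein thrombosis and other conditions. The synopsis adds known risk factors for raised intracranial or intraocular pressure. Sections 3.1.1, 4.1 and 9.5 apply these criteria by review of the EPIC record.

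**Risk.** Section 9.4.2 covers embarrassment, confidentiality and discomfort. Under discomfort it cites the contact-sports approval, says that "there are no adverse risks for the indicated population", and continues: "However there is a possibility that patients will feel discomfort when wearing it". Section 9.4.4 acknowledges the change of use: "Given that the device is approved by the FDA in a different setting, that is, contact sports".

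**Safety data.** Section 3.1.2 has ten minutes of monitoring after fitting. Section 3.1.3 has a general daily question on discomfort or adversity. Sections 5.3 and 7.1.3 tell participants to stop and report if they notice a significant change or new symptoms. The schedule of procedures marks adverse events at Visit 1 and during home use, but not at Visit 2. Section 8.1 says adverse events are monitored throughout. Section 6.2 anticipates none, and Section 6.3.3 opens with "Adverse events are not expected".

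**The concern.** The protocol ties one hazard to both the device and the disease, and builds much of its exclusion list around it. The section that sets out the risks to participants does not mention that hazard. The reassurance it gives comes from a different group of users.

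Two things are at stake. The first is that the risk assessment does not tell its readers how the stated pressure effect bears on patients with tinnitus. The second is the quality of the safety data. If a pressure-related symptom occurs at home, its capture depends on the participant volunteering it in answer to a general question. At Visit 2 no adverse event item is scheduled at all. Section 9.4.3 says the pilot data are meant to justify later trials, so a zero count obtained this way would be hard to interpret.

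**Working it through.** The plan states no figure on this point, so there is none to reproduce. The check is mainly a comparison of sections.

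**1. Is the pressure effect in the risk section?** Section 1.1 says the collar raises intracranial pressure, with the qualifier that it does so safely. Section 9.4.2 has three headings (psychological, confidentiality, discomfort), and pressure appears under none of them. The statement about no adverse risks is limited to the indicated population. Coming straight after the reference to contact sports, that most naturally means athletes. So the section does not deny a pressure risk in tinnitus patients; it leaves the question out.

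**2. Does eligibility close the gap?** Partly. Sections 3.3.2 and the synopsis remove a wide set of pressure-related conditions. The check is a chart review, and the documents describe no study procedure that looks for raised pressure. What remains is the unrecognised case. The documents do not say how common that is.

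**3. How would a symptom be recorded?**

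| Stage | Safety capture in the protocol text | Pressure symptom named? |
|---|---|---|
| Visit 1 | Supervised fitting, 10 minutes of monitoring | No |
| Home, 14 days | Daily general question; stop-and-report instruction | No |
| Visit 2 | Refitting under supervision; no adverse event mark in the schedule | No |

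The empty Visit 2 cell does not fit Section 8.1, since the collar is worn again at that visit (Sections 3.1.4 and 4.1.3).

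**4. Context: what a zero count would mean.** Section 6.3.3 plans exact two-sided 95% intervals for everyone entered at Visit 1. Section 3.2.2 expects about 22 enrolled to give 20 evaluable. With zero events the upper limit is 1 − 0.025^(1/n):

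- n = 22 (the safety set): 1 − 0.025^(1/22) = 15.4%
- n = 20 (evaluable): 1 − 0.025^(1/20) = 16.8%

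The documents give no event rate, so the rates p below are assumptions. The chance of at least one event among 22 is 1 − (1 − p)^22:

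| Assumed p | Chance of at least one event |
|---|---|
| 1% | 20% |
| 2% | 36% |
| 5% | 68% |
| 10% | 90% |

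All of these assume that every event is reported. If only a fraction c is reported, the 15.4% limit applies to c × p. The limit on p itself is then 15.4%/c, which is larger. The documents give no value for c.

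**The case against.** The best defence is that the protocol recognises the pressure hazard and manages it through eligibility. The exclusions are broad, the abstract refers to a thorough ENT work-up, and Section 9.4.4 rests minimal risk on following the FDA's recommendations, contraindications included. New pressure symptoms would also fall within the stop-and-report wording of 5.3 and 7.1.3. All of that is fair. It narrows the gap to unrecognised cases and to how reliably symptoms are recorded. It does not explain why 9.4.2 is silent or why Visit 2 has no adverse event item.

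A reader might infer more than the documents support:

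- **That the sections flatly contradict each other.** They do not. The statement in 9.4.2 is limited to the indicated population, and 1.1 says safely.
- **That the tinnitus is often due to intracranial hypertension.** Section 1.3 gives no frequency and names anatomical variation as the alternative.
- **That only known raised pressure is excluded.** The list is much longer.
- **That the collar raises intraocular pressure.** No section says so; intraocular conditions appear only among the exclusions.
- **That Section 8.2 expects no adverse events.** It says this of serious adverse events only; the broader expectation is in 6.2 and 6.3.3.
- **That participants are never asked about pressure symptoms.** The appendix says the scales and documents were filed with the IRB. The REDCap forms are not in the reviewed text, so their wording cannot be checked.
- **That the 15.4% or 16.8% limit measures the fault.** It would hold for any event in a study of this size, and better questions would not change it.

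**Conclusion.** The point holds as an omission with a cheap remedy. Section 9.4.2 relies on experience in another population and does not discuss, for tinnitus patients, the pressure effect described in 1.1. The protocol text specifies only general symptom capture, and the schedule leaves Visit 2 without an adverse event item.

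The size of the risk cannot be put in numbers, because neither the share of unrecognised raised pressure nor the completeness of reporting is given. The binomial figures show only that zero reports among 22 participants would leave rates up to 15.4% compatible with the data, and that this limit depends on full capture. The finding on capture assumes that the daily form follows the general wording of the protocol. If the form already lists pressure symptoms, that part reduces to saying so. The silence of 9.4.2 and the Visit 2 gap in the schedule remain in either case.

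**What to change.** 1. Reconcile 9.4.2, and the expectation of no adverse events in 6.2 and 6.3.3, with 1.1, 1.3 and 3.3.2 by discussing the intracranial pressure effect in the tinnitus population.
2. Add a few fixed yes/no pressure-symptom items, chosen by the study physician, to the existing daily REDCap form, or state in the protocol that the form already has them.
3. Mark an adverse event item at Visit 2 in the schedule, to agree with 8.1.
4. Tabulate these responses under 6.3.3 for all subjects entered at Visit 1, with the exact intervals already planned. Section 4.2.1 deletes the records of withdrawn subjects apart from adverse events, so say whether the item responses, including negative ones, are kept for this table.

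The cost is some wording, a few items on an existing form and one more table. The downside is that prompted items will record more minor events, so the table should show prompted and volunteered reports separately. No wear, stopping or eligibility rule is proposed.

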#### 9.4.3 Potential Benefits of Trial Participation

Direct Benefits: Immediate symptom and quality of life improvement while wearing the collar during the study.

Indirect Benefits: contributing to widespread approval and access of color are used for venous pulsatile tinnitus population if effective in relieving symptoms by generating pilot data that will be used to justify clinical trials.

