#### ABSTRACT

#### Context: (Background)

Tinnitus is a medical condition with a wide variety of causes that is characterized by the perception of sound, often described as ringing or buzzing, without an external stimulus. Venous pulsatile tinnitus is a specific subtype of tinnitus with limited treatment options beyond surgical correction of underlying vascular defect. The clinical diagnostic hallmark of venous pulsatile tinnitus is relief of symptoms with light compression of the ipsilateral external jugular vein by the physician.

Objectives: (primary and important secondary objectives)

This study seeks to pilot an evaluation of whether an external jugular vein compression collar approved by the FDA for contact sports can provide symptomatic relief of venous pulsatile tinnitus. Furthermore, the study will pilot quality of life impacts of the device. Study Design:

This is a non-blinded, interventional, prospective single cohort pilot study in which participants will be asked to evaluate the effect of wearing the collar, if any, on tinnitus symptoms. Secondary effects such as adherence, comfort, and quality of life while wearing the device will also be evaluated.

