#### Surveys and Scales:

The Tinnitus Handicap Inventory (THI) is a 25-item validated survey that evaluates the degree of impact a patient's tinnitus has on their quality of life. It is currently the first line survey for systemic impacts of tinnitus and is attached at the end of this proposal. In addition, NIH validated patient reported outcome measurement information system (PROMIS) questionnaires on anxiety, depression, physical function, and satisfaction will be administered before and after the treatment period to evaluate the collar's broader impact on patient quality of life (see end of proposal). Additionally, a custom tinnitus intensity scale modeled after the numerical pain scale with be used to assess relief. Lastly, a single item Likert scale inquiring about use of the collar when symptoms present will be applied to evaluate adherence.

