# 2 STUDY OBJECTIVES

The purpose of the study is to determine the preliminary efficacy of an internal jugular vein compression collar for treating pulsatile tinnitus. Pilot data, if demonstrative of efficacy, will be used to apply for a multicenter grant.

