# 4.1.2 Between Visit (at home) phase

Patient wears collar for <4 hours total while awake for symptomatic relief as needed

Patient reports daily average tinnitus intensity with and without collar, length of use, and any adverse events through REDCAP email/text link

Continues daily for 14 days

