#### 6.4 Sample Size and Power

For the principal endpoint, the tinnitus intensity scale ranges from 1-10. Assuming an average tinnitus intensity of 5 and a standard deviation of plus or minus 2 (such that 95% of the venous pulsatile tinnitus population has tinnitus intensity between 1 and 9). Intensity scale measurements will be averaged across individual submissions and across participants. With 16 paired evaluations per participant and 20 participants total, that creates 320 non collar tinnitus intensity measures.

Setting an alpha of p=.05 and a power of 0.8 (beta=0.2), we expect a minimum effect of a 1 point decrease between the no collar and collar measurements. To be conservative, we will preserve the 2 point standard deviation assumed for the baseline measure to apply to the collar relief measure. These parameters allow us to evaluate the viability of our sample size.

$$n_{g} \doteq (z_{lpha/2} + z_{eta})^{2} rac{\sigma_{1}^{2} + \sigma_{2}^{2}}{(\mu_{1} - \mu_{2})^{2}}$$

Where n is the number of analyses that will allow our minimum effect size to be significant Substitution lends us the following

 $\begin{array}{l} n_{\rm g} = (1.96 {+}~ 0.8416)^{2*} (2^2 {+} 2^2) / (2)^2 \\ n_{\rm g} = 15.86 \end{array}$ 

Not only is our overall study well in exceeding the number of intensity measurement differences needed to measure a significant effect; we will be able to assess the significant effect within each participant, given that each participant will complete both the with and without collar scales a total of 16 times. This gives our study strong internal and external validity.

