#### 9 STUDY ADMINISTRATION

# 9.1 Treatment Assignment Methods

There will be no randomization or blinding of participants.

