#### 9.6 Informed Consent/Assent and HIPAA Authorization

The principal investigator or one of the physician investigators not responsible for the patient's care will approach a patient meeting exclusion and inclusion criteria in person during one of their regular visits at UNC Meadowmont outpatient clinic. This will occur in the examination room after the patient's care provider has stepped out. At this point the patient will be asked about their interest in hearing about and possibly participating in a study that could help their tinnitus. If the patient acquiescence, the team member will then explain the study as well as its potential direct benefits and risks to the patient, emphasizing that the ultimate goal is scientific advancement instead of improved care. If the patient acquiesces, the consent forms and HIPAA form will be shared and explained to them. If they are still willing to participate, they will sign the forms and become a participant.

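### Section 6.4 claims strong internal and external validity that an unblinded, self-rated, single-clinic cohort does not have, and Section 9.4.3 states the hypothesis as an unconditional benefit

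*Combined protocol and SAP*

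**What the plan says.** **Design.** The Abstract states: "This is a non-blinded, interventional, prospective single cohort pilot study". Section 9.1 adds: "There will be no randomization or blinding of participants". Section 3.2.2 plans for one clinic and 20 evaluable participants.

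**Outcome.** Under Surveys and Scales (Section 1.3), the primary measure is described as follows: "a custom tinnitus intensity scale modeled after the numerical pain scale with be used to assess relief". For the home phase, Section 4.1.2 says: "Patient reports daily average tinnitus intensity with and without collar, length of use, and any adverse events through REDCAP email/text link". Sections 4.1.2 and 9.4.2 leave home wear to the participant's need for relief, so the on and off periods are not assigned. Section 6.3.2 tests the with/without difference by a one-sided t test.

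**Validity claim.** Section 6.4 argues from the 16 paired ratings per participant and concludes: "This gives our study strong internal and external validity".

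**Benefit wording.** Section 9.4.3 reads: "Direct Benefits: Immediate symptom and quality of life improvement while wearing the collar during the study". Under Section 9.6, "the patient will be asked about their interest in hearing about and possibly participating in a study that could help their tinnitus". Staff then explain the potential direct benefits and the risks, and stress that the aim is to advance science and not to improve care.

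**Use of the result.** Section 2 says: "Pilot data, if demonstrative of efficacy, will be used to apply for a multicenter grant".

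**The concern.** The participant supplies both numbers in every pair and knows which one belongs to the collar. Someone who expects the collar to help can report a lower with-collar rating even if the collar does nothing. The test compares the whole difference with zero, and the plan reads that difference as relief from the collar. Nothing in the documents separates the two: there is no sham, no assigned on/off order, no measure of expectation and no stated caveat.

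The Section 6.4 sentence goes further than staying silent on this limit. It credits the design with the property it lacks, and gives repeated measurement as the reason. A reader of the pilot report or the grant application could then take a small p-value as sound evidence that the collar works. The unqualified benefit statement in Section 9.4.3 matters for the same reason: it is the study hypothesis, and if it carries over into what participants hear, it may add to the bias that the design cannot remove.

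**Working it through.** **1. The plan's own figure.** Section 6.4 gives n = 15.86. Its substituted formula, (1.96 + 0.8416)² × (2² + 2²) / 2², gives 7.849 × 8 / 4 = 15.70, which agrees closely. This uses a difference of 2, although the text names 1 point; with 1 point the formula gives 62.79. That mismatch is a separate matter and the present point does not depend on it. A sample-size formula of this kind deals with random error only and says nothing about bias.

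**2. What 16 repeats do.** Write one participant's difference on occasion j as d + b + e_j, where d is the collar effect, b a constant expectation shift and e_j random error. The mean over 16 occasions is d + b + (mean of e_j).
- Random error: if the e_j are independent, their SD falls by √16 = 4.
- Expectation: 16b / 16 = b, so it is unchanged.

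The test addresses d + b = 0, not d = 0. Less noise around d + b makes a significant result more likely when d = 0 and b > 0.

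**3. External validity.** Section 6.4 counts 16 × 20 = 320 no-collar ratings. They come from about 20 people at one clinic. More ratings per person do not widen the population sampled.

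**4. Illustration of size.** Inputs from the plan: n = 20, one-sided test, alpha 0.05, SD 2 in each condition. Assumed, and not in the documents: d = 0, b = 0.5 or 1 point, and the SD of the participant-level difference. With correlation r between conditions, that SD is √(4 + 4 − 8r): 2.83 at r = 0 and 2 at r = 0.5. The values 1.5 and 1 are added because averaging over repeats can lower it.

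The chance of significance is the upper tail of a noncentral t with 19 df beyond the 5% critical value, with noncentrality b√20 / SD. For b = 1 and SD = 2 the noncentrality is 4.472 / 2 = 2.236 and the chance is 0.695.

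| SD of difference | b = 0.5 | b = 1 |
|---|---|---|
| 1.0 | 0.695 | 0.996 |
| 1.5 | 0.418 | 0.890 |
| 2.0 | 0.286 | 0.695 |
| 2.83 | 0.189 | 0.452 |

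The nominal rate is 0.05. For either shift the chance rises as the SD falls, as step 2 implies. The larger shift equals the 1-point minimum effect named in Section 6.4.

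**5. Benefit wording side by side.** In Section 9.4.3 the direct benefit carries no condition, while the indirect benefit in the same section depends on the collar proving effective. Section 9.6 uses conditional language. The unqualified sentence is out of line with both.

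**The case against.** The study is openly a non-blinded pilot. Section 2 calls its aim preliminary efficacy, and Section 9.4.3 says the data will be used to justify clinical trials. Each participant is compared with their own no-collar rating, which deals with stable differences between people. There is also a physical rationale: Section 1 reports that manual jugular compression relieves venous tinnitus. All of this stands. An open-label single-cohort pilot is an acceptable design, and this point does not call for a sham arm here. None of it supports the validity sentence, because the within-person comparison is still made by someone who knows the condition, and the rationale makes the hypothesis plausible without testing it.

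A reader might infer that participants are promised improvement. The documents do not show this. The consent form was not available for review. Section 9.4.3 is protocol text under a heading about potential benefits. Section 9.6 speaks of a study that could help, of potential direct benefits, and of science ahead of care. The statement in Section 9.4.4 that the collar is likely to work is risk-benefit reasoning and is not shown to reach participants. So the wording may add to expectation; that it does so is not established.

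A reader might also take the table as this trial's false-positive rate. It is not, since the shifts and the SDs of the difference are assumed. Finally, the with/without argument concerns the primary endpoint. The quality of life scales are before/after measures, and it does not carry over to them unchanged.

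**Conclusion.** The point holds in this limited form. The claim of strong internal and external validity in Section 6.4 is unsupported: repeated ratings reduce random error but not expectation bias, and about 20 patients from one clinic do not establish wide applicability. A significant one-sided result cannot by itself distinguish a collar effect from expectation, and no section says so. The direct-benefit sentence in Section 9.4.3 should be conditional.

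The conclusion about Section 6.4 needs no numerical assumption. The range of 19% to over 99% shows only that a shift no larger than the plan's own minimum effect could often produce a significant result. The documents do not support reading the point as a finding that the design is unacceptable, that participants are misled, or that the collar has no effect.

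**What to change.** 1. In Section 6.4, delete the validity sentence. State that the primary result is an unblinded within-person difference between with-collar and without-collar ratings that includes any expectation effect, so a positive result supports a controlled trial and is not by itself evidence of efficacy. Qualify the reference to demonstrated efficacy in Section 2 to match.
2. Reword Section 9.4.3 and the approach in Section 9.6 so that benefit is possible but neither known nor assured. Check that the consent form says the same.
3. Put a neutral instruction on the REDCap rating page: ratings may be higher, lower or the same with the collar.
4. Optional: in the objectives, replace language about determining whether the collar relieves symptoms with language about estimating the within-person change.

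The cost is wording in the protocol, the recruitment and consent material and the rating page. No participants, visits or analyses are added. The neutral wording may reduce expectation but leaves the comparison unblinded, which is why item 1 is needed as well. The downside is a more modest stated claim.
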